7.3 Liver safety monitoring

Not applicable.

7.4 Renal safety monitoring

Not applicable.

7.5 Reporting of study treatment errors including misuse/abuse

Not applicable as no study treatment is provided. In cases of drug/device misuse and abuse local regulations, processes and legislation on reporting should be followed.

7.6 Pregnancy reporting

Not applicable. Local laws and regulations for reporting adverse drug reactions should be followed.

8 Data review and database management

8.1 Site monitoring

Before study initiation, at a study center initiation visit or at an Investigator's meeting, a Novartis representative will review the protocol and eCRFs with the Investigators and their staff. During the study, the field monitor will visit the study center regularly to check the completeness of patient records, the accuracy of entries in the eCRFs, the adherence to the protocol and to GCP and the progress of enrollment. Key study personnel must be available to support the field monitor during these visits.

The Investigator must maintain source documents for each patient in the study, consisting of case and visit notes (hospital or clinic medical records) containing demographic and medical information, laboratory data, and the results of any other tests or assessments. All information on CRFs must be traceable to these source documents in the patient's file. The Investigator must also keep the original ICF signed by the patient (a signed copy is given to the patient).

The Investigator must give the monitor access to all relevant source documents to confirm their consistency with the CRF entries. Novartis monitoring standards require full verification for the presence of informed consent, adherence to the inclusion/exclusion criteria, documentation of SAEs, and of data that will be used for all primary variables.

Additional checks of the consistency of the source data with the CRFs are performed according to the study-specific monitoring plan. No information in source documents about the identity of the patients will be disclosed.

8.2 Data collection

Designated investigator staff will enter the data required by the protocol into the Electronic Case Report Forms using fully validated software that conforms to US CFR 21 Part 11 requirements. Designated investigator site staff will not be given access to the EDC system until they have been trained. During data entry, data is checked for completeness and correctness via automatic plausibility checks. In case of data discrepancies an appropriate error message will be shown asking the Investigator to confirm or correct data. The Investigator must certify by electronic signature that the data entered into the Electronic Case Report Forms are complete and accurate. After database lock, the investigator will receive copies of the patient data for archiving at the investigational site.

8.3 Database management and quality control

The CRO data management working on behalf of Novartis or Novartis staff will review the data entered into the eCRFs by investigational staff for completeness and accuracy and instruct the site personnel to make any required corrections or additions. Queries are sent to the investigational site using an electronic data query. Designated investigator site staff is required to respond to the query and confirm or correct the data. Concomitant medications and procedures and non-drug therapies entered into the database will be coded using the WHO Drug Reference List, which employs the Anatomical Therapeutic Chemical classification system. Medical history and adverse events will be coded using the Medical

dictionary for regulatory activities (MedDRA) terminology. Local laboratory data regarding hemoglobin, creatinine and/or potassium will be entered into the eCRF if available within the sites' clinical routine. The occurrence of relevant protocol deviations will be determined. After these actions have been completed and the database has been declared to be complete and accurate, it will be locked and made available for data analysis. Any changes to the database after that time can only be made after written agreement by Novartis Development management.

8.4 Data Monitoring Committee

Not required.

8.5 Adjudication Committee

Not required.

9 Data analysis

The analysis will be conducted on all subject data at the time the trial ends. Any data analysis carried out independently by the investigator should be submitted to Novartis before publication or presentation.

Details of the planned statistical analysis will be described in detail in a separate statistical analysis plan.

9.1 Analysis sets

Analysis of baseline variables will be carried out on all patients who signed the study information consent (Enrolled Set).

Analysis regarding the prospective period of the study will be carried out on all patients entering into this study period – the respective patient set will be labeled Follow-up Set.

9.2 Patient demographics and other baseline characteristics

Summary statistics will be provided for demographics and other baseline characteristics described in [Section 6.2](#). Additionally, age groups (< 65, ≥ 65 to < 75, ≥ 75 to < 85, ≥ 85 years) and BMI calculated as weight (kg) / (height (m))² will be displayed. Classification of patients as “clinically stable” will be provided.

Continuous variables will be summarized using n, mean, median, standard deviation, minimum, maximum, and categorical variables will be summarized using frequency and percentage.

Baseline characteristics will be displayed for all patients in the Enrolled Set, stratified by the variable “inclusion into the prospective period of the study”.

9.3 Treatments

No study treatment will be provided in this trial.

Prior and concomitant medication will be presented separately for medications due to HF and other medication. Concomitant medications are defined as any medications administered at or after the enrollment date into the study, otherwise the medication is defined as prior.

The assessment of the patient's treatment at every visit with respect to the adherence to the time-actual ESC guidelines will be provided (definition see [Section 2.1](#)).

Separate summaries will be provided for all treatment changes advised by the cardiologist and the implementation of these changes to the actual treatment of the patient by the primary care physician.

Additionally, statistical models might be considered for analyzing associations between ESC guideline adherence of treatment regimens and possible covariates. Such models will be described in detail in the Statistical Analysis Plan.

The analysis of the patients' treatment will be performed for all patients in the Enrolled Set (where applicable) in the Follow-up Set. All treatment analyses will additionally be performed stratified by country/region.

9.4 Analysis of the primary variable(s)

The primary objective in this study is to assess if NT-proBNP measurement-guided cardiologist-referral of CHF patients, who are currently judged by their primary care physician as being clinically stable, leads to optimization of HF treatment, defined as adherence to level I-A treatment recommendations of the current ESC guidelines for the treatment of HF. Therefore the aim of the primary analysis is to estimate the proportion of patients switching from a non-ESC guideline recommendations-adherent HF treatment at baseline to a guideline-adherent treatment after referral to a cardiologist.

9.4.1 Variable(s)

The variables used for the primary analysis are the assessment of the patient's treatment at baseline (A1) and the assessment of the patient's treatment at visit 2 (A2) with respect to the adherence to the current ESC guidelines.

9.4.2 Statistical model, hypothesis, and method of analysis

The analysis yielding to the primary objective will be performed by estimating the proportion of patients who are switched to an ESC guideline recommendation-adherent regimen after referral to a cardiologist based on all referred patients whose treatment does not adhere to these recommendations. A respective 95%- confidence interval (CI) will be provided for this proportion.

Cross-tabulation between the variables A1 and A2 will be displayed showing further absolute and relative frequencies, including the proportion of patients being treated in accordance to the ESC guideline recommendations already at baseline (i.e. before referral), the proportion of patients receiving ESC guideline-adherent treatment after the referral to the cardiologist and the rate of patients who remain on a therapy regimen that does not adhere to ESC guideline-recommendations after referral over all patients without ESC guideline-adherent treatment. Respective 95%-CIs will be provided for the estimates.

The analysis of the primary endpoint will be performed in the Follow-up Set.

9.4.3 Handling of missing values/censoring/discontinuations

No imputation of missing values will be performed. The analysis of the primary variable will be based on all available cases, i.e. on all patients for whom assessments of treatment before and after cardiologist referral are available. Additionally, proportions based on all patients including missing values for the treatment after referral will be presented.

9.4.4 Sensitivity analyses

In order to detect possible country effects or effects of further subgroups and allow for a site and patient profiling, stratified analyses of the primary endpoint will be performed at least for the following subgroups:

- Country/region cluster information for site
- Sex
- Age groups
- NT-proBNP levels

Please refer for details to the Statistical Analysis Plan.

9.5 Analysis of secondary variables

Analysis of secondary variables will be performed in the Follow-up Set and additionally stratified by the assessment of the treatment before and after referral to a cardiologist (*ESC non-conform/ESC conform, ESC non-conform/ESC non-conform, ESC conform/ESC conform, ESC conform/ESC non-conform*).

9.5.1 Patient reported outcomes

Health related quality of life as measured by the patient reported outcomes EQ-5D-5L and KCCQ.

The KCCQ instrument includes several domains. Only the domains that address HF symptoms and physical limitations will be analyzed. The clinical summary score of KCCQ is computed as the mean of the following available domain scores:

- Physical limitation score
- Total HF symptom score

Minimal clinical improvement according to the KCCQ will be defined for each of the two domain scores as an improvement of at least 5 points compared to baseline ([Flynn, Lin et al. 2012](#)).

The EQ-5D-5L consists of five domains and one visual analogue scale. This instrument assesses morbidity, self-care, usual activity, pain, and anxiety and depression of patients on a five-point rating scale ranging from *1=no problems* to *5=extreme problems*. A continuous utility index will be derived from these dimensions.

Quantitative outcomes such as KCCQ sub-domains, EQ-5D visual analogue scale and EQ-5D utility index will be displayed in terms of descriptive statistical parameters such as valid n, mean, SD, minimum, median and maximum at each visit.

Furthermore, for visit 2 the change from baseline and for visit 3 the change from baseline and from visit 2 will be calculated and displayed.

In case of ordinal or dichotomous measures such as EQ-5D dimensions and KCCQ response distributions in terms of absolute and relative frequencies will be provided for the single visits.

9.5.2 Safety variables

Adverse events (AEs) will be coded by means of the Medical Dictionary for Regulatory Activities (MedDRA). Incidence rates of AEs and Serious Adverse Events (SAEs) due to study related procedures based on “preferred terms” and “system organ class” will be displayed. Additionally, all AEs will be individually listed.

9.5.3 Biomarkers

NT-proBNP will be collected in all patients at baseline and visit 3 (only for patients who have entered the prospective period). Summary statistics for quantitative and qualitative data will be provided for each visit. The change in NT-proBNP level from baseline to visit 3 will be calculated and presented describing the amount of quantitative change and the number of patients with increase/decrease of NT-proBNP blood level.

9.7 Interim analyses

An interim analysis describing baseline characteristics and data collected at Visit 1 can be performed. Details are described in the Statistical Analysis Plan.

9.8 Sample size calculation

The study is powered to estimate the proportion of patients switching from a non-ESC guideline recommendations-adherent treatment to regimen adhering to these recommendations after referral to a cardiologist based on all patients who at baseline are judged by their primary care physician to be clinically stable and show NT-proBNP levels ≥ 600 pg/ml.

Based on the data from Dahlstrom et al ([Dahlstrom, Hakansson et al. 2009](#)), showing that only 20% of patients followed by primary care physician receive both Renin-Angiotensin System inhibitors and beta-blockers at a dose $\geq 50\%$ of the recommended, we conservatively assume 20% as the percentage of CHF patients that will be treated in accordance to the ESC guidelines (i.e. prescription of any drugs with level I-A recommendation for a given patient's

clinical status at a dose of > 50% of the recommended daily dose) at baseline (Visit 1). In addition, we assume that after referral to a specialist (Visit 2), the proportion will increase to 30% ([Maggioni, Anker et al. 2013](#)). Although there are no data in the literature measuring the clinical impact of increasing guideline-adherence of treatment in HF, it has been clearly demonstrated that a 10% increase in acute coronary syndrome is clinically highly significant. In fact, for every 10% increase in guideline-adherence at a hospital center, the in-patient's mortality odds ratio falls by a corresponding 39%. Similarly, for every 10% increase in appropriate dosing, the patient's mortality odds ratio falls by a corresponding 18% ([Mehta, Chen et al. 2015](#)).

We further assume that around 25% of patients without ESC guideline recommendations-adherent treatment at baseline (i.e. prior to referral to a cardiologist) will receive optimization (i.e. ESC guideline adherent treatment) of their HF treatment post referral to the cardiologist. This proportion can be estimated with a precision of $\pm 2\%$ using a 95%-CI by including 1,728 patients into the analysis; for subgroup analyses (e.g. on country level) the range of a 95%-CI increases, however it is still possible to estimate the proportion with a precision of $\pm 5\%$ for subgroups of 300 patients.

Considering of the above assumptions, a number of 2,160 patients who enter the prospective period of the study (i.e. referral to a cardiologist) is required. It is further assumed, based on unpublished data from chronic heart failure registries (data on file), that at least around 60% of patients treated by primary care physicians will have NT-proBNP levels ≥ 600 pg/ml at baseline. This in turn leads to the calculation that, in order to obtain 2,160 patients in the prospective period of the study, 3,600 consecutive patients will need to be enrolled for visit 1 (baseline).

Assuming an expected drop-out rate of 10% of patients, 4,000 patients will be enrolled of whom 2,400 will enter into the prospective period.

The sample size calculation was performed with nQuery Advisor version 7.0 'using Table POC0-1.

10 Ethical considerations

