2.4 Objectives and related endpoints

Table 2-1 Objectives and related endpoints

OBJECTIVE	Endpoint Title, Description and Reporting Time Frame for analysis and Unit of Measure	Stat Analysis Section
Primary		
To assess if NT-proBNP measurement-guided cardiologist-referral of CHF patients, who are currently judged by their primary care physician as being clinically stable, leads to optimization of HF treatment, defined as adherence to level I-A treatment recommendations of the current ESC guidelines for the treatment of HF.	Title: Change of the proportion of clinically stable patients whose therapy regimen adheres to ESC guideline recommendations before and after specialist referral. Description: Assessment of patients' treatment regimen with respect to ESC guideline adherence at baseline (Visit 1) and after referral to a specialist (visit 2); the change between both visits will be calculated to reflect the proportion of patients for whom optimization was deemed necessary and implemented. For definitions of clinically stable patients and adherence to current ESC guidelines see Section 2.1 . Units of Measure: Bivariate absolute and relative frequency distributions including 95%-confidence intervals. Time Frame: Baseline, Visit 2	Section 9.4

OBJECTIVE	Endpoint Title, Description and Reporting Time Frame for analysis and Unit of Measure	Stat Analysis Section
Secondary		

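### Protocol 9.8's 20%, 30% and 25% do not reconcile unless adherence is lost at a rate nobody states, and the net before-after change has no pre-specified paired interval

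*Protocol*

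**What the plan says.** **Planning figures (Protocol 9.8).** Baseline adherence is assumed to be 20%. The protocol then states "we assume that after referral to a specialist (Visit 2), the proportion will increase to 30" per cent. Separately, "around 25% of patients without ESC guideline recommendations-adherent treatment at baseline" are assumed to be optimized after referral. The sample size is the number needed to estimate that last proportion to about ±2 percentage points. Relevance is argued by analogy: "a 10% increase in acute coronary syndrome is clinically highly significant".

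**Endpoint (Protocol 2.4, Table 2-1).** The title is "Change of the proportion of clinically stable patients whose therapy regimen adheres to ESC guideline recommendations before and after specialist referral". The description says "the change between both visits will be calculated to reflect the proportion of patients for whom optimization was deemed necessary and implemented". The units are "Bivariate absolute and relative frequency distributions including 95%-confidence intervals".

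**Analysis (Protocol 9.4.2 and 9.4.3).** The primary estimate is the proportion switched among patients non-adherent at baseline, with a 95% CI. Further single proportions with their own CIs include baseline adherence and "the proportion of patients receiving ESC guideline-adherent treatment after the referral to the cardiologist". The available-case analysis is based "on all patients for whom assessments of treatment before and after cardiologist referral are available".

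**SAP 7.4.2 and 7.13.** Adherence is tabulated at each visit. A2 is tabulated among patients non-adherent at Visit 1 and again among those adherent at Visit 1, on level 1 (drug type, primary) and on level 2 (drug type and dose, sensitivity), with CIs for the proportions in the primary analysis. SAP 7.13 replaces the A1 by A2 cross table with separate tables.

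**The concern.** Two things do not fit together.

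First, the three planning figures describe the same referred patients, so any two of them, together with a loss rate, fix the third. No loss rate is given. Movement from adherent to non-adherent appears only as a reporting stratum (Protocol 9.5, SAP 7.1).

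Second, the relevance argument and the primary number are different quantities. A rise from 20% to 30% is net: gains minus losses. The switch proportion counts gains only, and only among baseline non-adherent patients. The same switch rate is compatible with quite different net changes. Loss of adherence is possible on the SAP's own scale: in Table 4-2 a patient with LVEF above 35% is classed as adherent only if not on an MRA, so a regimen change can move a patient out of the adherent category.

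At stake is interpretation. A reader who sets a 25% switch rate against the 10-point benchmark is comparing unlike things, and the quantity that would be comparable has no planned interval.

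**Working it through.** **Inputs.** All are from Protocol 9.8: baseline adherence 20%, Visit 2 adherence 30%, switch rate s = 25%, precision ±2 points, 1,728 in the analysis, 2,160 in the prospective period, 60% above the NT-proBNP threshold, 10% drop-out.

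**1. The plan's own figure.** The Wald half-width at n = 1,728 is 1.96 × √(0.25 × 0.75 / 1,728) = 2.04 points, which is ±2 after rounding (exactly ±2.00 would need 1,801). The chain reproduces: 1,728 / 0.80 = 2,160; 2,160 / 0.60 = 3,600; 3,600 / 0.90 = 4,000; 4,000 × 0.60 = 2,400. The first step shows that the 20% and the 25% refer to the same patients: the 1,728 are the 80% of 2,160 who are non-adherent at baseline. The 30% is used nowhere in the chain.

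**2. Consistency.** With L the share of baseline-adherent patients who lose adherence:

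Visit 2 adherence = 0.20 × (1 − L) + 0.80 × s

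- s = 0.25, L = 0: 0.20 + 0.20 = 40%.
- To reach 30% with s = 0.25: L = (0.40 − 0.30) / 0.20 = 50%.
- To reach 30% with L = 0: s = (0.30 − 0.20) / 0.80 = 12.5%.

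The protocol's figure is approximate, so vary it. Setting Visit 2 adherence to 30% gives L = 4s − 0.5: 30% loss at s = 20%, 50% at s = 25%, 70% at s = 30%. Rounding of the 25% does not remove the conflict. Nor does drop-out: counting 10% as non-adherent gives 0.90 × 40% = 36%.

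**3. Effect on N.** If 12.5% were the right switch rate, n = 1,728 would give ±1.56 points, and ±2 would need 1,051. The planned N is not short on this account.

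**4. Net change and its paired interval.** With g the share gaining and h the share losing adherence, among all patients with both assessments:

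d = g − h; half-width = 1.96 × √((g + h − d²) / n), n = 2,160

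| Switching | Loss | g | h | Visit 2 adherence | Net change, 95% half-width |
|---|---|---|---|---|---|
| 25% | 0% | 0.20 | 0 | 40% | +20.0 ± 1.7 |
| 25% | 50% | 0.20 | 0.10 | 30% | +10.0 ± 2.3 |
| 12.5% | 0% | 0.10 | 0 | 30% | +10.0 ± 1.3 |

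Rows 1 and 2 have the same switch rate but net changes that differ by a factor of two. Rows 2 and 3 have identical margins (20% and 30%), and therefore identical separate CIs at each visit, yet their paired half-widths are ±2.3 and ±1.3. Two marginal CIs cannot supply the interval for the difference.

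**5. What is and is not planned.** Protocol 9.4.2 and SAP 7.4.2 give intervals for single or conditional proportions. The one interval method named in SAP 7.1, Clopper-Pearson, is for a single proportion. No paired difference or interval for one appears in either document. Under SAP 7.1 percentages exclude missing values parameter by parameter, so the by-visit percentages may also rest on different patients and need not subtract to the paired change.

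**The case against.** The best defence is that nothing in the design or the primary analysis turns on the 30%. N rests on 25%, ±2 points and the 80% non-adherent share. Apart from the title, the target is stated consistently: the description in Table 2-1, Protocol 9.4 and Protocol 9.8 all point to the switch proportion, and it has a 95% CI. SAP 7.4.2 tabulates A2 in both baseline strata, so all four cells are available and a reader can compute the paired interval unaided. The 10% figure is borrowed from another disease as a per-increment association, not set as a success threshold. All of this stands, and it keeps the point minor.

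It does not remove the point. Protocol 9.8 presents 30% as what this study's own proportion will become, not as an external benchmark, so the three figures ought to agree. The endpoint title and the relevance argument both concern the net change, and its interval is left to the reader.

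Stronger readings that the documents do not support:

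- *The sample size is wrong because of the 30%.* The 30% does not enter it.
- *The primary endpoint has no analysis, or losses are concealed.* The switch proportion has a CI and the losses are tabulated.
- *The sponsor expects half of adherent patients to lose adherence.* That is only what the algebra requires at exactly 25% switching; no loss rate is asserted.
- *The net effect on the SAP's primary level 1 scale could be nil or negative.* Neither document gives a baseline, switch or loss rate for that definition, so no figure can be put on it. The MRA rule in Table 4-2 shows that loss is possible, not how frequent it is.

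**Conclusion.** The point holds, as a minor one. The 20%, 30% and 25% in Protocol 9.8 cannot all be true without loss of adherence in about half of baseline-adherent patients (30% to 70% for switching of 20% to 30%). With no loss, the 25% implies 40% after referral, and the 30% implies 12.5% switching. The sample size is unaffected.

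The consequence is for interpretation. The net change, which the relevance argument uses and the endpoint title names, is 20 or 10 points at the same 25% switch rate with 0% or 50% loss, and its paired interval is not pre-specified.

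The arithmetic and the absence of a paired interval are certain. The half-widths are planning-stage illustrations: they take n = 2,160 with both assessments, the Wald form, and loss rates chosen to span the conflict. The study stopped early (SAP 4.2) and the achieved number is not given, so actual intervals will differ. The 20% is also not strictly a figure for the SAP's level 2, because its source covers renin-angiotensin inhibitors and beta-blockers only, with no MRA rule.

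**What to change.** In SAP 7.4.2, beside the switch proportion, add:

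> The change in the proportion adherent (A2 minus A1) will be estimated with a paired 95% CI in Follow-up Set patients with both assessments, for guideline adherence level 1 and level 2.

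Name the interval method, since Clopper-Pearson does not apply to a paired difference. Report this row wherever the result is set against the 10-point benchmark. The switch proportion stays as the primary estimate.

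In SAP 7.13, or the addendum that SAP 7.12 provides for, add one sentence: the protocol's 30% after referral is not consistent with 20% at baseline and 25% switching unless adherence is lost, and should not be used as the expected post-referral proportion. There is no need to choose a new set of planning figures now that recruitment has ended; it would change no result.

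Cost: two table rows computed from counts already planned, and one sentence of text. No further patients, data or visits.
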